8.2 Sample Size Determination

The difference in the proportion of subjects in the test and reference treatment groups who achieve "treatment success" defined as "total disappearance of all warts within all treated areas" at four days (\pm 5 days) after the last day of the last cycle of treatment will be evaluated using a two-sided 90% confidence interval. The therapeutic equivalence of the test and reference products will be established if the confidence bounds of the 90% confidence interval are contained within the limits of -0.20 to +0.20. The results in the PP population will be considered definitive for therapeutic equivalence with those in the mITT population considered supportive.

Table 5. Sample Size Rationale

Equivalency margin	Power (%)	CI (%)	Sample Size mITT* (test: RLD: placebo)	Sample Size PP* (test: RLD: placebo)	
20%	85%	90%	392 (168:168:56)	350 (150:150:50)	

^{*} Sample sizes were calculated assuming: 40.0% success rate for active treatment, and 15.0% success rate for vehicle; 20% equivalency margin (EQ).

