	The difference in the proportion of subjects in the test and reference treatment groups who achieve "treatment success" defined as "total disappearance of all warts within all treated areas" at four days (\pm 5 days) after the last day of the last cycle of treatment will be evaluated using a two-sided, continuity-corrected 90% confidence interval. The therapeutic equivalence of the test and reference products will be established if the confidence bounds of the 90% confidence interval are contained within the limits of -0.20 to +0.20. The results in the per-protocol (PP) population will be considered definitive for therapeutic equivalence with those in the modified Intent-To-Treat (mITT) population considered supportive.
	Superiority will be assessed through continuity-corrected Z-tests comparing each active treatment to placebo. If both the test and RLD success proportions are statistically significantly greater than the placebo proportion (p<0.05, two-sided) then they will be considered to be superior to the placebo. The results in the mITT population will be considered definitive for superiority with those in the PP population considered supportive.
	Subjects discontinuing due to "treatment failure", defined as worsening of condition and requiring alternate or supplemental therapy for the treatment of external anogenital warts during the study, will be included in the PP population analysis as treatment failures, and provided with effective treatment. Subjects discontinued prematurely from the study for any other reason (i.e., noncompliance, or withdrawal of consent, etc.) will be excluded from the PP population, but included in the mITT population, using Last Observation Carried Forward (LOCF).
	SAFETY ANALYSIS

Protocol: 16-POD-001 Version 2.0, 15-Jan-2018

Safety data analysis will include local application site reaction scores (erythema, dryness, burning/stinging, erosion, edema, pain, itching and bleeding), reported adverse events, vital signs and concomitant medication assessments summarized by treatment group and time point of collection, when appropriate.
Descriptive statistics (arithmetic mean, standard deviation (SD), coefficient of variation (CV), median, minimum, and maximum) will be calculated for quantitative safety data as well as for the difference from baseline, when appropriate.

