5.3 Sample Size Considerations

Approximately 413 subjects (177 in each active arm and 59 in placebo group) will be enrolled to obtain at least 392 mITT subjects (168 in each active treatment arm and 56 in placebo group) and to complete 350 PP subjects (150 in each active arm and 50 in placebo group). This sample size was calculated assuming that both active treatments would have equivalent success rates of 40% and placebo would have a success rate of 15%. This sample size will provide an overall probability of at least 0.9 of having the 90% Wald confidence interval, with Yates' continuity correction, of the difference between the test and reference success rates contained within the interval -0.20 to +0.20 in the PP population, in addition to establishing that the success rates for both active treatments are statistically greater than that of the placebo arm (two-sided continuity-corrected Z-tests, $\alpha = 0.05$) in the mITT population.

mITT (T:R:Placebo)	Prob. of Superiority*	of Superiority* PP (T:R:Placebo) Prob.		Prob. of study success
168:168:56 (392)	0.98	150:150:50 (350)	0.92	0.90

*) Superiority analysis based on two-sided, α = 0.05, continuity-corrected Z-tests.

**) Bioequivalence (BE) analysis based on 90% confidence interval (CI) of the difference between Test and reference for proportions of subjects with treatment success, calculated by the Wald's method with Yates' continuity correction.

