7.4 Data Presentation Conventions

Continuous variables (e.g. age) are summarized using descriptive statistics (number of subjects with available data, mean, standard deviation (SD), coefficient of variation (CV), median, minimum and maximum). Categorical variables (e.g. race) are summarized using counts and percentages. Percentages are calculated using the total subjects per treatment group.

The following conventions are applied to all data presentations and summaries.

For continuous variables, all mean, median, and coefficient of variation values are formatted to one more decimal place than the measured value. Standard deviation values are formatted to two more decimal places than the measured value. Minimum and maximum values are presented with the same number of decimal places as the measured value.

For categorical variables, the number and percentage of responses are presented in the form XX (XX.X %) where the percentage is in the parentheses.

Date variables are formatted as DDMMMYYYY for presentation. Time is formatted in military time as HH:MM for presentation.

Confidential

Wherever possible, data will be decimal aligned.

P-values, if applicable, will be presented to 4 decimal places. If the p-value is less than 0.0001 then it will be presented as <0.0001.

Unless otherwise stated, any statistical tests performed will be 2-sided at the 5% significance level.

The table and listing shells and table of contents as part of this SAP provide the expected layout and titles of the tables, listings and figures. Any changes to format, layout, titles, numbering, or any other minor deviation will not necessitate a revision to the SAP nor will it be considered a deviation from planned analyses. Only true differences in the analysis methods or data handling will necessitate such documentation. The appropriate listings supporting the tables will be included and are not specified in the individual sections throughout the document.

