9.1.2 Superiority Analysis

Superiority will be assessed through continuity-corrected Z-tests comparing each active treatment to placebo. If both the test and RLD success proportions are statistically significantly greater than the placebo proportion (p<0.05) then they will be considered superior to the placebo. The results in the mITT population will be considered definitive and those in the PP population will be considered supportive.

For each treatment (Test and RLD) the Hypothesis to be tested is:

 $H_0: p_t - p_p \leq 0$

 $H_a: p_t - p_p > 0$

Where p_t = Proportion of cure for Treatment, and p_p is proportion of cure for Placebo.

The rest of the formulation is the similar to the one for Equivalence assessment, using 95% Confidence Interval. For testing the superiority, the following SAS code will be used:

proc freq data = dataset;

Confidential

```
tables treat*outcome/ riskdiff (Equal correct);
run;
```

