Source: <Dataset>Listing: 16.1.3.1Snapshot Data DD-MMM-YYYYProgram Name: <Pgm name>Date: YYYY-MM-DD Time: HH:MM:SSProgrammer: <Programmer Initials>

Repeat for PP and Safety populations

Protocol: 16-POD-001 Version 2.0, 15-Jan-2018

Confidential

Table 14.2.1.1.1 Summary of Treatment Success by Visit, PP Population

	Test Product N =	Reference N =	Placebo N =	All Subjects N =
Visit	n (%)	n (%)	n (%)	n (%)
Visit 3 (Day 7)	xx (xx.xx)	xx (xx.xx)	xx (xx.xx)	xx (xx.xx)
Visit 4 (Day 14)	xx (xx.xx)	xx (xx.xx)	xx (xx.xx)	xx (xx.xx)
Visit 5 (Day 21)	xx (xx.xx)	xx (xx.xx)	xx (xx.xx)	xx (xx.xx)
Visit 6 (Day 28)	xx (xx.xx)	xx (xx.xx)	xx (xx.xx)	xx (xx.xx)
EOS	xx (xx.xx)	xx (xx.xx)	xx (xx.xx)	xx (xx.xx)

Treatment success: total disappearance of all warts within all treated areas.

Test Product: Podofilox Topical Gel 0.5%

Reference: Condylox® Gel 0.5%

Placebo: vehicle that matches the test product

Source: <dataset></dataset>	Listing: 16.2	Snapshot Data DD-MMM-YYYY
Program Name: <pgm name=""></pgm>	Date: YYYY-MM-DD Time: HH:MM:SS	Programmer: < Programmer Initials>

Protocol: 16-POD-001 Version 2.0, 15-Jan-2018

Confidential

Table 14.2.2.1.1 Bioequivalence Test for Proportion of Treatment Success between Test and Reference Products

		Test Product	Reference	Difference (SE)	90% CI
Population		n (%)	n (%)		
РР	EOS	xx (xx.xx)	xx (xx.xx)	x.xx (x.xxx)	(x.xx, x.xx)
mITT		xx (xx.xx)	xx (xx.xx)	x.xx (x.xxx)	(x.xx, x.xx)
n: Number of subjec	ts who experienced treatm	nent success			
SE: Standard Error					
CI: Confidence Inter	val				
Test Product: Podofi	lox Topical Gel 0.5%				

Reference: Condylox® Gel 0.5%

Source: <Dataset>

Program Name: <Pgm name>

Listing: 16.2 Date: YYYY-MM-DD Time: HH:MM:SS Snapshot Data DD-MMM-YYYY

Programmer: < Programmer Initials>

Repeat as Supplemental Analysis including site 201 for PPs/mITTs

Protocol: 16-POD-001 Version 2.0, 15-Jan-2018

Confidential

Table 14.2.3.1.1Treatment Success, Superiority Test from Placebo

	Test Productn (%)	Reference n (%)	Placebo n (%)	Test vs. Placebo Diff (95% CI) p	Reference vs. Placebo- Diff (95% CI)
mITT	xx (xx.xx)	xx (xx.xx)	xx (xx.xx)	x.xx (x.xx, x.xx) x.xxxx	x.xx (x.xx, x.xx)
PP	xx (xx.xx)	xx (xx.xx)	xx (xx.xx)	x.xx (x.xx, x.xx) x.xxxx	x.xx (x.xx, x.xx)

n: Number of subjects who experienced treatment success SE: Standard Error CI: Confidence Interval *p*: Probability of lower bound of CI with Walt-Yate's continuity correction Test Product: Podofilox Topical Gel 0.5% Reference: Condylox® Gel 0.5%

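### SAP 5.3 overstates power: under the test it names, both-arm superiority is about 0.93 and overall success about 0.87, not 0.98 and at least 0.9

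*SAP*

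**What the plan says.** SAP 5.3 defines study success as a conjunction. For the PP population, the 90% continuity-corrected Wald interval for test minus reference must lie between the limits of ±0.20. The second condition, for the mITT population, is worded as follows: "in addition to establishing that the success rates for both active treatments are statistically greater than that of the placebo arm". It puts the probability of this at 0.9 or more: "This sample size will provide an overall probability of at least 0.9 of having the 90% Wald confidence interval". The table beneath gives superiority 0.98 (mITT 168:168:56), equivalence 0.92 (PP 150:150:50) and study success 0.90. Its footnote fixes the test: "Superiority analysis based on two-sided", alpha 0.05, continuity-corrected Z-tests.

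The SE of the superiority test is not given in 5.3. SAP 9.1.2 says only: "The rest of the formulation is the similar to the one for Equivalence assessment, using 95% Confidence Interval". The equivalence SE in 9.1.1 is unpooled.

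On sidedness, the SAP synopsis has "statistically significantly greater than the placebo proportion (p<0.05, two-sided" and SAP 7.4 sets the default: "any statistical tests performed will be 2-sided at the 5% significance level". SAP 9.1.2, however, writes one-sided hypotheses with p<0.05 and no stated side. The footnote to the Table 14.2.3.1.1 shell defines p as "Probability of lower bound of CI with Walt-Yate's continuity correction".

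Protocol 8.2, Table 5, gives 85% power for the same mITT and PP sizes, with the footnote assumption "40.0% success rate for active treatment, and 15.0% success rate for vehicle". It does not name the event that has 85% power.

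**The concern.** The product 0.98 x 0.92 is 0.90, so the stated overall figure depends on the superiority figure being right. A value of 0.98 looks high for two comparisons that both have to succeed against one placebo arm of 56 subjects, with a continuity correction. If 0.98 is too high, the stated overall probability is too high as well, and the risk of missing the study's success definition is understated. The protocol's 85% for the same design adds to the doubt, because a reader cannot tell which probability the sample size rests on.

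**Working it through.** **Inputs (SAP 5.3).** Success rates 0.40, 0.40 and 0.15; mITT 168:168:56; PP 150:150:50; two-sided alpha 0.05 with continuity correction; equivalence limits ±0.20. The equivalence interval and its correction are as printed in SAP 9.1.1.

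**1. Equivalence, stated 0.92.** The half-width at the assumed rates is 1.645 x sqrt(2 x 0.24/150) + (1/150 + 1/150)/2 = 0.0931 + 0.0067 = 0.0997. By normal approximation the power is 2Φ((0.20 − 0.0997)/0.0566) − 1 = 2Φ(1.773) − 1 = 0.924. Exact binomial enumeration gives 0.928. The stated figure reproduces.

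**2. One active arm against placebo.** Reject when (pA − pP) − c ≥ 1.96 SE, where c = (1/168 + 1/56)/2 = 0.0119.

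- Unpooled SE at the assumed rates: sqrt(0.24/168 + 0.1275/56) = 0.0609.
- Normal approximation: Φ((0.25 − 0.0119)/0.0609 − 1.96) = Φ(1.951) = 0.9745.
- Exact enumeration: 0.958 unpooled, 0.940 pooled.

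**3. Both active arms against placebo, stated 0.98.** The two comparisons share the placebo arm. Given the placebo count, the two active arms are independent, so the conditional rejection probability is squared and then averaged over the placebo distribution. In the normal approximation the correlation is (0.1275/56)/(0.24/168 + 0.1275/56) = 0.614.

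**4. Overall success, stated at least 0.9.** This was simulated with 2,000,000 trials (simulation SE 0.0002), with PP nested in mITT and the 18 extra mITT subjects per active arm succeeding at the same 40%.

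| Two-sided 0.05, continuity-corrected | One arm | Both arms | Both arms and equivalence |
|---|---|---|---|
| SAP 5.3 table | – | 0.98 | 0.90 |
| Exact, unpooled SE | 0.958 | 0.933 | 0.872 |
| Exact, pooled SE | 0.940 | 0.906 | 0.848 |
| Normal approximation, unpooled SE | 0.9745 | 0.956 | 0.889 |
| Normal approximation, pooled SE | 0.941 | 0.902 | 0.844 |

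(The last column of the two exact rows is the simulated joint probability.) Multiplying exact both-arm superiority by exact equivalence gives slightly less: 0.933 x 0.928 = 0.866 and 0.906 x 0.928 = 0.840. For that product to reach 0.90, both-arm superiority would have to be 0.90/0.928 = 0.970.

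**5. Calculations that come near the table.** None is the both-arm event under the labelled test.

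- One comparison only, unpooled normal approximation: 0.9745 x 0.9237 = 0.900.
- Both arms at one-sided 0.05, corrected, unpooled: normal approximation 0.979, and 0.979 x 0.9237 = 0.904. The exact values are 0.964 and 0.898 overall.
- Both arms, two-sided, without the correction, unpooled normal approximation: 0.972, and 0.902 overall.

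The documents do not show which calculation was used, so none of these is put forward as the cause.

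**6. All randomised subjects.** At 177:177:59 the labelled both-arm probability is still only 0.946 (unpooled) or 0.924 (pooled).

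**7. Protocol Table 5, 85%.** If this means equivalence alone, it differs from the SAP's 0.92. If it means overall success, it differs from the SAP's 0.90. It is close to the pooled joint value of 0.848, but nothing in the protocol says that is what it is.

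**The case against.** Several points can be made for the plan.

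- **The pooled figures are secondary.** SAP 9.1.2 points back to an unpooled SE, so the 5-point end of the range rests on an SE that the SAP does not indicate. This stands: 0.93 and 0.87 are the lead figures, and 0.91 and 0.85 are a sensitivity case.
- **Planning figures are often normal approximations.** On that basis, with the unpooled SE, the overall figure is 0.88 to 0.89 and the gap is only 1 to 2 points. That is true, but it is still below 0.9, and 0.956 is still below 0.98. The exact value is also the power the design actually has.
- **The 0.98 column may describe one comparison.** Its heading does not mention both arms, and 0.9745 x 0.9237 = 0.900 matches the last column. This is plausible, although 0.9745 rounds to 0.97. It would not rescue the claim, because the text of 5.3 requires both arms to succeed.
- **Sidedness is effectively settled.** The 95% interval in 9.1.2 and the two-sided default in 7.4 both imply a two-sided 0.05 test, and no passage sets a one-sided 0.05 level. This largely stands. What remains is loose wording in 9.1.2 and in the table footnote.
- **The protocol's 85% may be a minimum equivalence power.** Section 8.2 discusses only equivalence, so this is possible, but the vehicle rate in the table footnote leaves the event unclear.
- **This is a planning figure.** It does not affect the analysis. That is correct, and it limits the weight of the point without making the figure right.

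**Conclusion.** The concern holds. Under the test and the success definition in SAP 5.3, superiority of both arms has probability about 0.93 rather than 0.98, and overall success about 0.87 rather than at least 0.9. With a pooled SE the values are about 0.91 and 0.85. The overall shortfall is about 3 to 5 points exactly, or 1 to 2 points by unpooled normal approximation. No two-sided, continuity-corrected calculation reaches 0.9 for the conjunction.

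These results assume that the 40% and 15% rates hold in the mITT population. If all subjects in mITT but not in PP were failures (an assumption the documents do not make), both-arm superiority would fall to 0.889 unpooled or 0.837 pooled.

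This is a misstated power, not a failed design. It should be corrected because the assurance is wrong under its own label and the protocol gives a different number for the same sample sizes.

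**What to change.** 1. **SAP 5.3:** remove the claim of at least 0.9. Restate both-arm superiority and overall success, computed exactly or by simulation with the shared placebo arm: about 0.93 and 0.87 with the unpooled SE, or 0.91 and 0.85 if a pooled SE is intended. State the event, SE and method behind each figure.
2. **SAP 9.1.2:** print the superiority test statistic with its SE and continuity correction, and say that p<0.05 is two-sided.
3. **Table 14.2.3.1.1 footnote:** define p as the two-sided p-value of that test.
4. **Protocol Table 5:** name the event to which the 85% refers and reconcile it with SAP 5.3.

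The cost is wording in four places and a slightly less favourable stated probability. The restatement itself needs no extra patients. If 0.90 was a firm target, whether about 0.87 is acceptable is for the sponsor to decide and record.

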6 PLANNED ANALYSIS

The analysis planned in the SAP will be performed after the database lock. The Efficacy Analyses will be conducted as follow:

Protocol: 16-POD-001 Version 2.0, 15-Jan-2018

Confidential

- Superiority to placebo: "treatment success" rate occurring at four days (± 5 days) after the last day of the last cycle of treatment using the mITT study population (PP population considered as supportive) and LOCF.
- BE: "treatment success" rate between the test product and RLD treatment groups occurring at four days (± 5 days) after the last day of the last cycle of treatment must be within [-0.20, +0.20] for the dichotomous primary endpoint, using the PP study population (mITT population considered as supportive).

Due to GCP non-compliance of site 201, Sponsor decided to generate two sets of Efficacy Analysis:

- a Definitive Efficacy Analysis Set excluding site 201 and
- a Supplemental Efficacy Analysis Set including site 201.

Please see corresponding Note to File (NTF) dated 27 Feb 2019 in study documentation detailing the specifics of the GCP non-compliance of site 201.

7 GENERAL CONSIDERATION FOR DATA ANALYSIS AND HANDLING

7.1 General Summary Table and Individual Subject Data Listing

Summary tables and listings (e.g., post text tables and individual subject data listings are prepared according to ICH Guideline E3) include a "footer" providing explanatory notes that indicate as a minimum:

- 1. SAS program name.
- 2. Programmer initials.
- 3. Date of data extraction.
- 4. Date of output generation.

Post text tables also include reference(s) to the subject data listing(s) that supports the summary data. The data extraction date links the output to the archived database that is locked to ensure the replication of the results.

Post text tables will be organized with respect to treatment group and a column will be included to summarize all treated subjects. The order of drug presentation will be investigational drug

Protocol: 16-POD-001 Version 2.0, 15-Jan-2018

Confidential

first followed by the reference drug, then the placebo, then the vehicle control. A total column will appear as the last column. The summary tables clearly indicate the number of subjects to which the data apply and unknown or not performed are distinguished from missing data.

Summary tables for medications and medical conditions are coded according the WHO Drug Dictionary. Adverse event preferred terms and body/organ systems are coded using the MedDRA dictionary. The MedDRA dictionary can be used, as well, in the coding of signs and symptoms, medical history, physical examination abnormalities, and clinical diagnoses.

Supportive individual subject data listings, as a minimum, are sorted and presented by treatment group and subject ID. Listings also include visit number, visit date, and days relative to the initiation of double-blind treatment.

From left to right, the subject number, visit number, visit date, and relative day should appear.

All tables and listings must have explanatory notes that give, as a minimum, data extraction date, output generation date, complete program name and path where it is stored, CRF pages from which the data were obtained, and supportive listings or tables supported, as appropriate. The definition of all derived variables and decodes for coded data must appear in the notes. Due to space limitations, tables and listings may require a page of notes as a one-time preface to the output.

7.3 Data Management

Biorasi will create SDTM data sets and ADaM analysis data sets using (SAS®) software. Data analyses and summary tables wil be generated using SAS version 9.4 or above.

7.4 Data Presentation Conventions

Continuous variables (e.g. age) are summarized using descriptive statistics (number of subjects with available data, mean, standard deviation (SD), coefficient of variation (CV), median, minimum and maximum). Categorical variables (e.g. race) are summarized using counts and percentages. Percentages are calculated using the total subjects per treatment group.

The following conventions are applied to all data presentations and summaries.

For continuous variables, all mean, median, and coefficient of variation values are formatted to one more decimal place than the measured value. Standard deviation values are formatted to two more decimal places than the measured value. Minimum and maximum values are presented with the same number of decimal places as the measured value.

For categorical variables, the number and percentage of responses are presented in the form XX (XX.X %) where the percentage is in the parentheses.

Date variables are formatted as DDMMMYYYY for presentation. Time is formatted in military time as HH:MM for presentation.

Confidential

Wherever possible, data will be decimal aligned.

P-values, if applicable, will be presented to 4 decimal places. If the p-value is less than 0.0001 then it will be presented as <0.0001.

Unless otherwise stated, any statistical tests performed will be 2-sided at the 5% significance level.

The table and listing shells and table of contents as part of this SAP provide the expected layout and titles of the tables, listings and figures. Any changes to format, layout, titles, numbering, or any other minor deviation will not necessitate a revision to the SAP nor will it be considered a deviation from planned analyses. Only true differences in the analysis methods or data handling will necessitate such documentation. The appropriate listings supporting the tables will be included and are not specified in the individual sections throughout the document.

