5 STUDY DESIGN

5.1 Summary of Study Design

This is a multicenter, parallel group, randomized, double-blind, placebo-controlled trial with clinical endpoint comparing Podofilox Topical Gel 0.5% to Condylox[®] Gel 0.5% and a matching placebo. The study will be conducted among adult male and female patients with external anogenital warts.

On the following day after the Baseline visit (Day 1) the subject will apply the study drug on EAWs following the recommendations given during training at the clinic site. The treatment phase will consist of four weekly treatment cycles at a maximum, during which the drug will be applied twice a day (in the morning and at the bedtime) for 3 consecutive days, then discontinuing for 4 consecutive days. Study drug will thus be applied only on Days 1, 2, 3, 8, 9, 10, 15, 16, 17, 22, 23 and 24.

Study visits will occur on the seventh (7) day of each treatment cycle: on Day 7 (Week 1), Day 14 (Week 2), Day 21 (Week 3), and Day 28 (Week 4). Primary endpoint (total disappearance of all treated warts) will be evaluated during each of these visits. In case the primary endpoint is reached at any of the visits prior to the Day 28 visit, it will be considered the End of Study (EOS) visit – the Investigator will perform physical examination and repeat urine pregnancy test, and subject's participation will be considered complete. If total disappearance of warts is not achieved, a new treatment cycle will be initiated for a maximum of four cycles in total for the subject.

During each study visit, the Investigator will collect vital signs, evaluate EAWs for absence or presence, capturing the count of EAWs, record Local Application Site Reactions and adverse events (AEs), assess Patient's Diary Card completion and subject's compliance with the study drug application, review concomitant medication and confirm that there were no prohibited therapies applied since the last visit.

In the event the primary endpoint (total disappearance of all warts within all treated areas) has been achieved prior to the Day 28 visit, this visit will be considered End of Study (EOS) visit. In case a subject discontinues prematurely, the Investigator will conduct an Early Termination (ET) visit, capturing the reason for discontinuation and performing assessments of EOS visit.

Protocol: 16-POD-001 Version 2.0, 15-Jan-2018

Confidential

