7.6.5 Handling of Missing Data

No data will be imputed for the Safety population. Missing Data for Efficacy analyses will not be imputed for the PP population. However, if data is missing due to other than early termination because of treatment failure, it will be imputed as LOCF for the mITT population.

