	from Baseline	Absent	xx (xx.x)	xx (xx.x)	xx (xx.x)	xx (xx.x)
		Present	xx (xx.x)	xx (xx.x)	xx (xx.x)	xx (xx.x)
		Mild	xx (xx.x)	xx (xx.x)	xx (xx.x)	xx (xx.x)
		Moderate	xx (xx.x)	xx (xx.x)	xx (xx.x)	xx (xx.x)
		Severe	xx (xx.x)	xx (xx.x)	xx (xx.x)	xx (xx.x)

Table 14.3.7Summary of Site Reaction by Intensity and Visit, Safety Population

Repeat for Site reactions: dryness, burning/stinging, erosion, edema, pain, itching, and bleeding.

Then Repeat for visit 4, 5, 6 and EOS.

n: number of patients affected. Test Product: Podofilox Topical Gel 0.5% Reference: Condylox® Gel 0.5% Placebo: vehicle that matches the test product

Source: <Dataset>

Program Name: <Pgm name>

Listing: 16.3.7 Date: YYYY-MM-DD Time: HH:MM:SS

Protocol: 16-POD-001 Version 2.0, 15-Jan-2018

Confidential

	Overall Summary o	of Adverse Events, Safe	ety Population	
	Test Product (N=xxx) n (%)	Reference (N=xxx) n (%)	Placebo (N=xxx) n (%)	All Subjects (N=xxx) n (%)
Total number of AEs	XX	XX	XX	XX
Total number of SAEs	XX	XX	XX	XX
Total Number of TEAEs	XX	XX	XX	XX
Total Number of TESAEs	XX	XX	XX	XX
Number of Subjects with:				
At Least One TEAE	xx (xx.x)	xx (xx.x)	xx (xx.x)	xx (xx.x)
At Least One Related TEAE	xx (xx.x)	xx (xx.x)	xx (xx.x)	xx (xx.x)
At Least One Severe TEAE	xx (xx.x)	xx (xx.x)	xx (xx.x)	xx (xx.x)
At Least One TEAE Leading to				
Discontinuation	xx (xx.x)	xx (xx.x)	xx (xx.x)	xx (xx.x)
At Least One TEAE Leading to			× ,	
Death	xx (xx.x)	xx (xx.x)	xx (xx.x)	xx (xx.x)
At Least One TESAE	xx (xx.x)	xx (xx.x)	xx (xx.x)	xx (xx.x)
At Least One Related TESAE	xx (xx.x)	xx (xx.x)	xx (xx.x)	xx (xx.x)
At Least One Severe TESAE	xx (xx.x)	xx (xx.x)	xx (xx.x)	xx (xx.x)
At Least One TESAE Leading to		. ,		
Discontinuation	xx (xx.x)	xx (xx.x)	xx (xx.x)	xx (xx.x)

Table 14 3 8

(S)AE: (Serious) Adverse Event reported from signature of the Informed Consent Form to 30 days following the last study drug application. TE(S)AE: Treatment Emerging (Serious) Adverse Event reported during the treatment period (from the day of the first application of the study drug and up to the last visit). Test Product: Podofilox Topical Gel 0.5% Reference: Condylox® Gel 0.5% Placebo: vehicle that matches the test product

Source: <dataset></dataset>	Listings: 16.3.8.1 – 16.3.8.2 – 16.3.8.3	Snapshot Data DD-MMM-YYYY
Program Name: <pgm name=""></pgm>	Date: YYYY-MM-DD Time: HH:MM:SS	Programmer: < Programmer Initials>

Protocol: 16-POD-001 Version 2.0, 15-Jan-2018

Confidential

Table 14.3.8.1.1

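### Table 14.3.7 divides late-visit local-reaction counts by the whole arm although cleared subjects have left, which lowers the printed percentages most where clearance is highest

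*SAP*

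**What the plan says.** - **Denominator.** SAP 7.4, on categorical variables: "Percentages are calculated using the total subjects per treatment group". In the same paragraph, continuous variables are summarised on the "number of subjects with available data". So the SAP already uses two different bases, and the categorical one ignores whether a subject was examined.
- **Early exit.** SAP 5.1: "In case the primary endpoint is reached at any of the visits prior to the Day 28 visit", that visit becomes the End of Study visit and the subject's "participation will be considered complete". Protocol 3.1 has the same rule.
- **No imputation.** SAP 7.6.5: "No data will be imputed for the Safety population".
- **The table.** Table 14.3.7 gives n (%) of local reactions by score (Absent, Present, Mild, Moderate, Severe) at Baseline and Visit 3, with the instruction "Then Repeat for visit 4, 5, 6 and EOS". The footnote reads "n: number of patients affected". The shell has no N in its column heads, no number assessed per visit, and no row for subjects who were not assessed.
- **Planned clearance.** SAP 5.3 assumes 40% success in each active arm and 15% on placebo.

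**The concern.** Local reaction scores are the first-listed secondary endpoint (protocol 2.2.2), and the secondary objective compares them across test, RLD and placebo. Table 14.3.7 is the only planned summary table of the 0 to 3 scores. No table gives a subject's worst score.

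Following the stated rule, a subject cleared at Visit 3, 4 or 5 remains in the denominator for every later visit but in none of the rows. The printed percentage then mixes two things: how often examined subjects had a reaction, and how many subjects were still there to be examined. The second depends on efficacy and is planned to differ by arm. At late visits the active gels would look better tolerated against placebo than the examined subjects show, simply because more of their users have cleared and gone.

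**Working it through.** **The plan's own figure.** The documents state no by-visit reaction rate and no clearance by visit, so there is no printed figure for this point. The nearest stated figure that rests on 40% clearance is the 0.92 probability of equivalence in SAP 5.3 (150 per active arm, 90% continuity-corrected interval, limits ±0.20):

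- SE = √(2 × 0.4 × 0.6 / 150) = 0.0566
- 2Φ((0.20 − 1/150)/0.0566 − 1.645) − 1 = 0.924, and 0.928 by exact enumeration of the SAP's interval.

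The 0.92 reproduces, which confirms that 40% is the planning rate in use.

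**Inputs for Table 14.3.7**

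- p = clearance by arm: 0.40 active, 0.15 placebo (SAP 5.3).
- f = share of those clearances that occur before Visit 6. Not in the documents; taken from 0.25 to 1. Clearance spread evenly over the four post-baseline visits would give f = 0.75.
- r = reaction rate among subjects assessed at Visit 6. Not in the documents; set to 30% in every arm.
- Other attrition is taken as similar by arm. The planned loss from randomised to PP is 1 − 150/177 = 15.3% in each active arm and 1 − 50/59 = 15.3% on placebo.

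**Formula**

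Share of the arm still assessed at Visit 6 = 1 − p·f. Printed percentage under SAP 7.4 = r × (1 − p·f). Percentage on subjects assessed = r.

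| f | Active: share assessed | Placebo: share assessed | Active, printed | Placebo, printed | Difference (points) | Ratio |
|---|---|---|---|---|---|---|
| 0.25 | 0.90 | 0.9625 | 27.0% | 28.9% | −1.9 | 0.94 |
| 0.50 | 0.80 | 0.925 | 24.0% | 27.8% | −3.8 | 0.86 |
| 0.75 | 0.70 | 0.8875 | 21.0% | 26.6% | −5.6 | 0.79 |
| 1.00 | 0.60 | 0.85 | 18.0% | 25.5% | −7.5 | 0.71 |

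The ratio does not depend on r. An equal rate looks 6% to 29% lower, in relative terms, on active than on placebo. With subjects assessed as the denominator, every cell would read 30%.

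**What happens to the Absent row.** At f = 0.75 the Absent percentage prints as 70% × 0.70 = 49.0% on active and 70% × 0.8875 = 62.1% on placebo. On active, Present + Absent = 21.0 + 49.0 = 70.0%, not 100%. Both rows shrink by the same factor.

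**Test against RLD.** At 40% in both arms the factors are equal and the comparison is undisturbed. If clearance were 30% against 40%, an equal 30% rate would print as 25.5% against 24.0% (f = 0.5) and 21.0% against 18.0% (f = 1), lower in the arm that clears more.

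**What would cancel the active-placebo gap.** Placebo would need extra non-clearance losses of (1 − 0.15f) − (1 − 0.40f) = 0.25f of its group: 12.5 points at f = 0.5 and 25 points at f = 1.

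**The case against.** The strongest reply is that the table is less misleading than it looks. Present and Absent are separate rows, so their counts add up to the number assessed and the proper rate can be rebuilt. The rows visibly fail to reach 100%. There is an EOS block in which subjects who cleared early do appear. SAP 7.1 asks that tables show the number of subjects to which the data apply and separate not-performed from missing. Protocol 6.2.1.7 requires every application site reaction to be recorded as an adverse event, so reactions also enter the TEAE tables by severity on the full arm. SAP 10.1 makes safety reporting descriptive.

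Most of this stands, and it limits the consequence. A reader might infer that departed subjects are tabulated as reaction-free. They are not: they fall in neither Absent nor Present, and both rows are deflated together. But none of it changes the denominator rule. The SAP 7.1 convention is not carried into this shell, although other shells (for example 14.2.1.1.1 and 14.3.8) do print N. Adverse-event severity is graded on a different scale (protocol 7.2) from the 0 to 3 score. A percentage that must be rebuilt before it can be compared between arms should not be the one printed.

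A second objection is also fair. Subjects assessed at Visit 6 are those not yet cleared, a post-randomisation subset whose make-up can differ by arm. Changing the denominator corrects the arithmetic but does not make the late-visit comparison a randomised one. That is why a worst-score summary on the full Safety population is needed beside it.

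**Conclusion.** The point holds as a defect of presentation in a descriptive secondary safety table, and it should be corrected. The mechanism follows from the text alone. The direction, lower printed rates in the arms that clear more, also requires that other attrition be similar by arm, as planned. If withdrawals for treatment failure fall mainly on placebo, the gap narrows.

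The size is not fixed by the documents. At a 30% reaction rate the Visit 6 gap runs from 1.9 to 7.5 points over the range of f. Even clearance timing gives 5.6 points, which is one value in that range and not an estimate.

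Two stronger readings are tempting and are not supported:

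- **That the rule biases test against RLD.** At the planned equal clearance both are deflated equally. Distortion arises only if their clearance differs.
- **That the wart-count tables (14.2.4 to 14.2.6) share the fault.** The quoted rule governs categorical percentages. Those tables summarise continuous data on available subjects, print n at each visit and include an EOS block. Carrying a zero forward in PP would contradict SAP 7.6.5 ("Missing Data for Efficacy analyses will not be imputed for the PP population"), and mITT already uses LOCF.

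Neither the equivalence analysis nor the superiority analysis is affected.

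**What to change.** 1. In SAP 7.4, add an exception: by-visit local-reaction percentages use the number of subjects assessed at that visit.
2. In Table 14.3.7, print that number for each arm and visit, and add a row for subjects who completed early or were not assessed. State whether a clearing visit is tabulated under its visit number, under EOS, or both. If it goes under EOS only, the visit at which a subject clears is affected as well.
3. Add one table of each subject's worst post-baseline score per reaction, with the full Safety population of the arm as denominator.
4. Keep the whole-group denominator for cumulative treatment success (the 14.2.1 series) and for TEAE incidence, where it is appropriate.

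The cost is a few sentences in the SAP, one denominator, one row and one extra table. No new data are needed. SAP 7.4 itself says that true differences in data handling must be documented, so this belongs in the SAP before database lock.
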